#### *8.8.2.2 Adverse Events Categorized as Other in the INTERMACS-definition based on MedDRA*

All adverse events (AE) that were categorized as ‘Other’ in the INTERMACS definition will be summarized by system organ class (SOC) and preferred term; events that are not treatment emergent will be listed only. A patient will only be counted once per system organ class and once per preferred term within a system organ class. Patient counts and percentages and event counts as well as event rate per patient year will be presented in the following summaries.

1. All Other Treatment Emergent Site-Reported AEs by SOC and preferred term
2. All Other Treatment Emergent Site-Reported ADEs by SOC and preferred term
3. All Other Treatment Emergent Site-Reported Non-ADEs by SOC and preferred term
4. All Other Treatment Emergent Site-Reported ADEs by SOC and preferred term – Related to MVAD System
5. All Treatment Emergent Site-Reported Serious Other AEs by SOC and preferred term
6. All Treatment Emergent Site-Reported Serious Other ADEs by SOC and preferred term
7. All Treatment Emergent Site-Reported Serious Other non-ADEs by SOC and preferred term
8. All Treatment Emergent Site-Reported Serious Other ADEs by SOC and preferred term – Related to MVAD System
9. All Other Treatment Emergent Site-Reported AEs leading to outcome of fatal by SOC and preferred term
10. All Other Treatment Emergent Site-Reported AEs leading to exchange/explant of device by SOC and preferred term
  
11. All Other Treatment Emergent Adjudicated AEs by SOC and preferred term
12. All Other Treatment Emergent Adjudicated ADEs by SOC and preferred term
13. All Other Treatment Emergent Adjudicated Non-ADEs by SOC and preferred term
14. All Other Treatment Emergent Adjudicated ADEs by SOC and preferred term – Related to MVAD System
15. All Treatment Emergent Adjudicated Serious Other AEs by SOC and preferred term
16. All Treatment Emergent Adjudicated Serious Other ADEs by SOC and preferred term
17. All Treatment Emergent Adjudicated Serious Other non-ADEs by SOC and preferred term
18. All Treatment Emergent Adjudicated Serious Other ADEs by SOC and preferred term – Related to MVAD System
19. All Other Treatment Emergent Adjudicated AEs leading to outcome of fatal by SOC and preferred term
20. All Other Treatment Emergent Adjudicated AEs leading to exchange/explant of device by SOC and preferred term

Adverse events potentially related to study device are defined as a subset of adverse events with a relationship to study device of either possible related or related. Events with missing relationship assessment will be included as potentially related to study device.

No statistical inference will be performed on adverse events.

Listings will be presented by patient for all adverse events as well as for each INTERMACS definition, UADEs, SAEs, adverse events associated with death, and adverse events leading to study device explant/exchange.

### **8.8.3 Clinical Laboratory Evaluations**

Clinical laboratory test values at each scheduled visit and for change from baseline (screening) to visit will be summarized using descriptive statistics.

All clinical laboratory data will be presented in listings. Within each listing, laboratory values outside the normal ranges will be flagged as either high (H) or low (L). In addition, shift tables will be presented to display the shift in the normal range categories (L, normal [N], H) from baseline to the each visit.

### **8.8.4 Other Variables Related to Safety**

#### *8.8.4.1 Vital Signs*

Vital sign measurements at each scheduled visit and change from baseline (screening) will be tabulated with descriptive statistics, including 95% confidence intervals for the means, by time point. A MAP value > 85 mmHg following discharge will be flagged in the listing.

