### 9.1.5.2 IBPM, Mean Arterial Blood Pressure (MAP) Assessment Procedure and Documentation

#### General

From the Instructions For Use (IFU), the recommended MAP target for subjects supported by the MVAD System is  $\leq 85$  mmHg (as tolerated) for subjects using an automated cuff method and  $\leq 90$  mm Hg for subjects who use the Doppler/cuff method.

While both device approaches yield MAP values within approximately 5 mm Hg of arterial line measurements, the Doppler/cuff method appears to give slightly higher values in non-pulsatile patients and a small adjustment is provided.

Following discharge from the index hospitalization, all subjects are required to adhere to an IBPM plan, in addition to receiving standard follow up care. Prior to discharge, subjects/caregivers will be trained to take blood pressures and record values (Automated cuff or cuff/Doppler) in a Blood Pressure (BP) diary.

Following discharge, the blood pressure will be obtained twice a day for at least the first 3 months and continue until the subject is medically stable with blood pressure within the recommended values (defined as MAP measurements  $\leq 85/90$  mmHg) and as medically appropriate for the subject.

Stability (defined as MAP measurements  $\leq 85/90$  mmHg) and compliance with the IBPM plan will be assessed by HeartWare based on Time in Therapeutic Range analysis (TTR) at monthly intervals for the first 3 months post-discharge, although it is understood that blood pressure is volatile and continuous monitoring is an essential element of improved blood pressure management.

After continuous monitoring for the first 3 months post initial discharge regardless of re-hospitalizations, stable subjects will have quarterly (3 month) TTRs performed to assess compliance. For subjects who have not met the stability definition, monthly monitoring will continue for another 3 month period. This will be repeated as often as necessary until subjects are stable.

All blood pressure measurements, including those recorded in the patient diary as well as any intervention such as medication changes to maintain the blood pressure within the therapeutically recommended ranges will be documented in the eCRF.

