#### Method of Measurement

HeartWare will provide a blood pressure cuff and Doppler device for all enrolled MVAD subjects. It is anticipated that cuffs of different sizes will be required and a selection of cuffs of different size will be provided to sites.

The protocol for blood pressure measurements is similar to that currently used in the current HeartWare US ENDURANCE Supplemental Trial. It is simple, reproducible and requires only that subjects be divided into 2 groups: those that have a palpable radial pulse and those who do not. For subjects with a palpable radial pulse, a standard

method of blood pressure measurement will be employed, namely an automated cuff. The specific methodology is listed below:

1. If the subject has a palpable radial pulse (approximately 40% of subjects), a Blood Pressure Cuff (BPC) will be used to obtain blood pressure measurements (systolic and diastolic) and MAP calculated as follows:  
$$\text{MAP} = (\text{Systolic Blood Pressure} + [2 \times \text{Diastolic Blood Pressure}]) / 3$$
2. If the subject has no palpable radial pulse, a Doppler and BPC will be used and the opening pressure will be reported as MAP.

Measurement of mean arterial pressure is the goal and it is understood that cuff/Doppler pressures are expected to be 5 – 8 mm Hg higher than MAP measured by the automated cuff method. To adjust for this difference, the upper limit for MAP will be set at  $\leq 90$  mm Hg for cuff/Doppler subjects.

Sites will input raw blood pressure data (systolic, diastolic or Doppler pressures) into the eCRF and automated calculations will be performed within the database.

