### **6.6.4 Other Safety Variables**

#### *6.6.4.1 Vital Sign Measurements*

Vital sign measurements (systolic and diastolic blood pressure, mean arterial pressure (MAP), heart rate, respiratory rate, and temperature) are scheduled at the screening visit (baseline), Days 1- 3 post implant, and month 1, 3, 6, 12, 18, and 24. Change from baseline to each visit will be defined as the visit value minus the baseline value. Blood pressure will be managed to maintain MAP as tolerated at  $\leq 85$  mmHg (using an automated cuff method) or  $\leq 90$  mmHg (using the Doppler/cuff method) for at least 3 months after discharge and continue until the subject is medically stable.

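### SAP change in MAP has no same-method condition, so in listings and case studies a switch between cuff and Doppler can pass for a change in blood pressure

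*SAP*

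**What the plan says.** Protocol 9.1.5.2 (Method of Measurement) divides subjects by whether the radial pulse can be felt. With a palpable pulse, put at roughly 40% of subjects, MAP is calculated as (systolic + 2 × diastolic) / 3 from a cuff reading. Without one, "a Doppler and BPC will be used and the opening pressure will be reported as MAP". The same subsection states that "cuff/Doppler pressures are expected to be 5 – 8 mm Hg higher than MAP measured by the automated cuff method". The General subsection of 9.1.5.2 is looser: "the Doppler/cuff method appears to give slightly higher values in non-pulsatile patients and a small adjustment is provided". The protocol deals with the difference by setting a separate upper limit for each method (85 and 90 mmHg). The recorded value itself is not corrected.

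SAP 6.6.4.1 mentions both methods when it restates those limits, but it lists only one MAP variable and no Doppler variable. Its rule for change is: "Change from baseline to each visit will be defined as the visit value minus the baseline value". SAP 8.8.4.1 adds: "Vital sign measurements at each scheduled visit and change from baseline (screening) will be tabulated with descriptive statistics", by time point and with no mention of method.

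Two other SAP sections decide where this matters. Section 5.2, on changes from the planned analyses, says that the trial stopped early with fewer than 15 subjects, drops the summaries and substitutes a case study for each subject. Section 7.1 still plans listings of all CRF data together with derived variables.

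**The concern.** Two quantities that the protocol expects to differ at the same true pressure share one name, and the change score subtracts one from the other without asking which is which. A subject read by cuff before implant and by Doppler afterwards would appear to have a rise in pressure. A subject who regains a palpable pulse would appear to have a fall.

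Switches are foreseeable. The After Discharge part of Protocol 9.1.5.2 supplies every subject with both devices and training on both, and pulse status decides which is used. Protocol 5.2.6 says that the qPulse cycle may increase pulsatility, and 9.1.7 has it switched on once the subject is hemodynamically stable. Pulse status, and with it the method, can therefore change between visits.

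At stake is how an individual's MAP series is read. In a case study no averaging dilutes the error, and a method switch could be taken for an effect of pump support or of blood-pressure management.

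**Working it through.** **Inputs**

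- Offset d (Doppler opening pressure minus cuff MAP at the same true pressure): 5 to 8 mmHg, Protocol 9.1.5.2, Method of Measurement.
- Upper limits by method: 85 mmHg (automated cuff) and 90 mmHg (Doppler/cuff), Protocol 9.1.5.2 and SAP 6.6.4.1.
- Change rule: visit minus baseline, SAP 6.6.4.1.

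**The protocol's own figure.** The 5–8 mmHg is a stated expectation without supporting data, so it cannot be reproduced. Two things can be compared with it.

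- The gap between the limits is 90 − 85 = 5 mmHg, the low end of 5–8.
- The General subsection puts both methods within about 5 mmHg of an arterial line. Two such readings could differ by anything from 0 to 5 + 5 = 10 mmHg. This is compatible with 5–8 but does not establish it. The direction, Doppler higher, is the same in both places.

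**Effect on one subject.** Let D = 1 for a Doppler reading and D = 0 for a cuff reading. Then

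listed change = true change + d × (D at visit − D at baseline).

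With a true change of zero:

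| Baseline | Visit | Listed change (mmHg) |
|---|---|---|
| Cuff | Cuff | 0 |
| Doppler | Doppler | 0 |
| Cuff | Doppler | +5 to +8 |
| Doppler | Cuff | −5 to −8 |

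The error from one switch is thus at least as large as the 5 mmHg by which the protocol separates its two limits. A same-method condition brings it to zero.

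**Can the method be recovered?** Yes. Protocol 9.1.5.2 has sites enter raw systolic, diastolic or Doppler pressures. The hemodynamic table in 9.1.5.1 has a Doppler row of its own beside the auto-calculated MAP row, at screening, at Days 1–3 and at every monthly visit. In that table, the footnote that invokes the blood-pressure plan is attached only to the Month 1–24 column, so the method rule is not expressly extended to screening. That is a further reason why the baseline method may differ from the later one.

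**The case against.** The strongest reply is that the tables in SAP 8.8.4.1 will not be produced, because section 5.2 withdraws them and 8.8.4.1 is simply unedited text. This stands for the tables. It does not reach the listings of derived variables under section 7.1 or the case studies that section 5.2 introduces.

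A reader might go further and infer that the planned MAP means are biased by a known amount. Taking the protocol's 40% as the post-implant share with a pulse, 60% would be read by Doppler. If everyone had been read by cuff at screening, the mean change would be inflated by 0.6 × 5 = 3.0 to 0.6 × 8 = 4.8 mmHg. The documents do not support this. The means are no longer planned, the method mix at screening is not given, and no switching rate is given. If the screening mix were also 60% Doppler, the same formula would give (0.6 − 0.6) × d = 0.

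Nor does the SAP say that the methods are pooled; that is inferred from the absence of a split. The alternative reading, that MAP means only the calculated cuff value, would leave subjects without a palpable pulse with no MAP at all, since SAP 6.6.4.1 has no Doppler variable. Either reading calls for a clarifying sentence.

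It is also fair to say that a careful reader of full listings could work out the method from the raw entries. That limits the harm but does not correct a derived change value printed without its method.

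Finally, MAP is a descriptive safety variable: it is not among the listed secondary endpoints, and only survival carries a hypothesis test. This stands and sets the severity.

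**Conclusion.** The concern holds for individual subjects and is minor. As written, SAP 6.6.4.1 allows a change in MAP to be taken across two methods that the protocol expects to differ. A subject who switches would show a spurious change of about 5–8 mmHg, upward from cuff to Doppler and downward the other way. That size rests on the protocol's expectation alone, and its General subsection describes the difference only as slight. No group-level bias can be stated, because neither the screening mix nor the switching frequency is documented and the summary tables are withdrawn. The survival endpoints are not touched.

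A related mismatch should be settled at the same time. The listing flag in SAP 8.8.4.1 uses one threshold, above 85 mmHg, for every MAP value, whereas Protocol 9.1.5.2 and SAP 6.6.4.1 give a separate limit for each method. Those passages must be reconciled.

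**What to change.** In SAP 6.6.4.1 and 8.8.4.1:

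1. State which quantity fills MAP at each scheduled visit, and show the method (calculated cuff MAP or Doppler opening pressure) beside each value in listings and case studies.
2. Derive change from baseline only between readings by the same method, using the Doppler value from the screening row where one was recorded. Otherwise mark the change as not comparable.
3. If any table under 8.8.4.1 is still produced, split MAP by method. Bring the wording of 8.8.4.1 into line with section 5.2.

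The cost is a few sentences and one extra listing column; no new data are needed. The real downside is that some subjects will have no change value. In the worst case, with no Doppler reading at screening and 60% read by Doppler afterwards, about 0.4 × 14 = 5.6 of at most 14 subjects would keep one. Those with cuff pairs are also selected on having a pulse after implant, so they should not be read as representing the rest. Screening Doppler values, where they exist, remove most of this loss.

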#### *8.8.4.2 Hemodynamic Parameters*

Hemodynamic parameters at each scheduled visit and change from baseline (screening) will be tabulated with descriptive statistics, including 95% confidence intervals for the means, by time point.

#### *8.8.4.3 Echocardiogram Parameters*

Echocardiogram parameters that are continuous variables will be summarized using descriptive statistics, including 95% confidence intervals for the means, at each scheduled visit and change from baseline (screening) by time point. Categorical echocardiogram findings will also be tabulated by time point.

#### *8.8.4.4 Length of Operative Time*

Length of operative time in minutes will be summarized using descriptive statistics, including 95% confidence intervals for the means. The number and percentage patients with operative time will also be summarized by the following categories: 0 – <60 minutes, 60 – <120 minutes, 120 – <180 minutes, 180 minutes or more.

#### *8.8.4.5 Length of Initial Hospital Stay*

Length of initial hospital stay (LOS) overall, LOS in ICU, and LOS in the general ward will be summarized using descriptive statistics, including 95% confidence intervals for the

means. The number and percentage of patients with an initial hospital stay  $\leq 7$  days, 8-14 days, and  $> 14$  days will also be summarized.

#### 8.8.4.6 *Re-Hospitalization*

The number and percentage of patients with re-hospitalization after the initial hospitalization will be tabulated by category of stay: 1, 2, and 3 or greater. The number of re-hospitalizations will also be summarized using descriptive statistics. Cumulative length of re-hospitalization after initial hospital stay (overall LOS), LOS in ICU, and LOS in general ward will be summarized using descriptive statistics, including 95% confidence intervals for the means. Overall LOS, LOS in ICU, and LOS in general ward will also be summarized by counts and percentages for each of the following categories:  $\leq 7$  days, 8-14 days, and  $> 14$  days.

#### 8.8.4.7 *Transplant*

The number and percentage of patients with transplantation will be tabulated. Time to first transplantation relative to initial implant will be summarized using descriptive statistics, including 95% confidence intervals for the means. Also, the time to first transplantation relative to initial implant in the following categories will be tabulated:

- Transplant occurred  $\leq 30$  days after implant
- Transplant occurred  $\leq 180$  days after implant
- Transplant occurred  $> 180$  days after implant

Time to first transplantation will be presented graphically as a Kaplan-Meier curve. If a patient had explants for recovery, exchanges (to a device other than MVAD® Pump) prior to transplantation, and any withdrawal or lost to follow-up will be censored at the time of this event date. For each patient that remains alive on device, time to first transplantation will be censored at the time of last contact date known to be alive (contacts considered in the determination of last contact date would include but not limited to scheduled visit dates, adverse event dates, and last known alive date).

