## 9.2 Device Explant

In the event that the MVAD Pump is explanted (i.e. death, transplant, recovery, device exchange) observations should be documented in the eCRF. A discharge summary may be requested by HeartWare.

At explant, the MVAD Pump and the incision sites should be inspected for:

- Pump condition prior to explant,
- Pericardial
- Sewing Ring condition,
- Outflow Conduit condition and position,
- Driveline status,
- Blood pump housing condition.

Any identified unusual findings are to be reported on the eCRF. Photographs can be taken of the MVAD Pump, cannula, driveline, or any anomaly at the explant.

The MVAD Pump should be briefly rinsed with saline then placed in formaldehyde for at least 2 days. After removal from the formaldehyde allow the pump to thoroughly dry and package as directed for return.

HeartWare will provide an Explant Kit that is designed for transportation of used health care products. Packaging instructions will be included in each Explant Kit.

In case the HeartWare Plug is used to seal the cored ventricle upon pump removal for recovery, the following Anticoagulation regimens are recommended:

- Warfarin for 3 months post plug insertion. Maintain INR at 1.8 to 2.0.
- Low dose ASA for 3 months and then re-evaluate

Anticoagulation regimens after implant of the HeartWare Plug have not been evaluated in clinical studies.

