#### 8.8.4.8 *Explant*

Number and percentage of patients with an explantation will be tabulated. Time to first explantation relative to initial implant will be assessed using descriptive statistics (sample size (N), mean and 95% confidence intervals for the means, minimum, maximum, median, and standard deviation). Also the time to first explantation relative to initial implant in the following categories:

- Explant occurred  $\leq 30$  days after implant
- Explant occurred  $\leq 180$  days after implant

- Explant occurred > 180 days after implant

The number and percentage of patients who had their LVAD device replaced will be tabulated. The number and percentage of patients who received a new HeartWare MVAD® device will also be tabulated. The number and percentage for reasons for explanation will be tabulated. Since patients can have multiple explants, the reasons for explantation will include all reasons. Therefore the percentages may add up to more than 100%.

Time to first explantation will be presented graphically as a Kaplan-Meier curve. Any withdrawal or lost to follow-up will be censored at the time of this event date. For each patient that remains alive on device, time to first explantation will be censored at the time of last contact date known to be alive (contacts considered in the determination of last contact date would include but not limited to scheduled visit dates, adverse event dates, and last known alive date).

Time to first exchange will be presented graphically as a Kaplan-Meier curve. If a patient had transplant or explants for recovery, and any withdrawal or lost to follow-up will be censored at the time of this event date. For each patient that remains alive on device, time to first exchange will be censored at the time of last contact date known to be alive (contacts considered in the determination of last contact date would include but not limited to scheduled visit dates, adverse event dates, and last known alive date).

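### The Kaplan-Meier curves for first transplant and first exchange censor competing exits and have no rule for death on device; the explant curve leaves open whether death is an event

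*SAP*

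**What the plan says.** Transplantations and explants are secondary endpoints 12 and 13 (Protocol 6.4). For each curve the SAP names the method and some of the censoring.

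- **Transplant (SAP 8.8.4.7).** "Time to first transplantation will be presented graphically as a Kaplan-Meier curve". Recovery explants and exchanges to a device other than the MVAD are censored when they occur "prior to transplantation, and any withdrawal or lost to follow-up will be censored at the time of this event date". A last-contact rule follows, which begins: "For each patient that remains alive on device, time to first transplantation will be censored at the time of last contact date known to be". It reaches only patients who are still living on the pump.
- **Explant (SAP 8.8.4.8).** "Time to first explantation will be presented graphically as a Kaplan-Meier curve. Any withdrawal or lost to follow-up will be censored", with the same last-contact rule. No other exit is named.
- **Exchange (SAP 8.8.4.8).** "Time to first exchange will be presented graphically as a Kaplan-Meier curve. If a patient had transplant or explants for recovery", that date is a censoring time, as are withdrawal and loss, again with the last-contact rule.

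None of the three mentions death, a competing-risk method or cumulative incidence. Both sections also tabulate the number and percentage of patients. SAP 6.6.4.7 and 6.6.4.8 set the denominator for these as all patients with a device implanted.

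On what an explant is, Protocol 9.2 opens with "In the event that the MVAD Pump is explanted (i.e. death, transplant, recovery, device exchange", so death heads the list of circumstances. Protocol 9.4.9 includes mortality among the reasons for explantation.

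**The concern.** Kaplan-Meier treats a censored patient as someone who could still have the event later, at the same rate as those left at risk. That suits withdrawal, loss and end of follow-up. It does not suit an exit that removes the patient from MVAD support. A transplanted patient cannot later have the MVAD exchanged. After recovery explant or exchange to another device, the schedule in Protocol 17.1.2 follows only survival status. Censoring these exits makes one minus Kaplan-Meier estimate incidence in a setting where the other exits never occur. That is higher than the proportion of implanted patients who actually have the event.

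Death on the pump is the largest such exit under the plan's own assumptions, and it has no rule. A programmer must choose between censoring deaths, counting them as events, dropping those patients, or keeping them in the risk set. These choices give different curves. For explant, the protocol's wording invites counting them as events.

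At stake is the reading of two secondary endpoints. Even with complete follow-up, a curve could show a visibly higher incidence than the table beside it.

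**Working it through.** **The plan's own figures.** The SAP gives no expected incidence for transplant, explant or exchange. The figures nearby are the sample size and the survival assumptions in SAP 4.5. The sample size reproduces. With n = 57, success needs at least 46 alive at 6 months (exact one-sided alpha 0.0486, power 0.862) and at least 37 alive at 24 months (alpha 0.0397, power 0.837). Nothing below touches these.

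**Inputs.**
- Deaths on device: 1 − 0.85 = 15% by 6 months and 1 − 0.70 = 30% by 24 months (SAP 4.5). SAP 7.3 counts only death with the pump in place as failure and takes other exits at their status at the procedure. So 30% is the crude proportion dying on the pump.
- True 24-month event incidence T: not in the documents. Assumed range 5% to 40%.

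**Formula.** Let X be the total crude incidence of the competing exits that are censored. If the cause-specific hazards stay in constant ratio over the interval,

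1 − KM = 1 − (1 − T − X)^(T/(T + X)).

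Example with T = 0.30 and X = 0.30 (deaths censored): 1 − 0.40^0.5 = 0.368.

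**Two-interval version.** Constant hazards place too few deaths early. In that example, deaths by 6 months are (1 − 0.40^0.25)/2 = 10%, against the plan's 15%. So the formula is applied separately to 0–6 and 6–24 months, with deaths at 15% in each interval and a quarter of the events assumed by month 6. Example with T = 0.20:
- At 6 months, KM = 0.80^(0.05/0.20) = 0.9457, so 5.0% plots as 5.4%.
- At 24 months, KM = 0.9457 × (0.50/0.80)^(0.15/0.30) = 0.7477, so 20% plots as 25.2%.

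| True 24-month incidence | Plotted, one interval | Plotted, two intervals | Ratio, two intervals |
|---|---|---|---|
| 5% | 6.0% | 6.2% | 1.25 |
| 10% | 12.0% | 12.5% | 1.25 |
| 20% | 24.2% | 25.2% | 1.26 |
| 30% | 36.8% | 38.2% | 1.27 |
| 40% | 49.7% | 51.6% | 1.29 |

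**Lower end of the range.** Take 30% instead as the mortality if nobody left by another route: death hazard d = −ln(0.70)/2 = 0.178 per year. With event hazard h, true incidence is h/(h + d) × (1 − exp(−2(h + d))) and the curve shows 1 − exp(−2h). At h = 0.10 that is 15.3% true against 18.1% plotted, a ratio of 1.18. For h from 0.025 to 0.30 the ratio is 1.19 down to 1.17, or 0.8 to 6.5 points.

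**The part that does not depend on the rule for death.** Assume 10% exchanged, 20% transplanted and 30% dead at 24 months. Censoring only the transplants, as SAP 8.8.4.8 instructs, with deaths kept in the risk set, gives X = 0.20 and 1 − 0.70^(0.10/0.30) = 11.2%. Censoring deaths too gives X = 0.50 and 1 − 0.40^(0.10/0.60) = 14.2%. The true value is 10%.

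**Explant curve.** If death counts as an explant event there is no competing death, but the curve adds the two. With 20% removals and 30% deaths it reaches 50%. If death is not an event, the missing rule arises here as well.

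**The case against.** The strongest objection is SAP 5.2. Version 2.0 reports early stopping with fewer than 15 subjects and replaces summaries with case studies. A Kaplan-Meier curve is a summary, so these three are probably never drawn. That stands, and it takes away most of the practical effect. But SAP 8.8.4.7 and 8.8.4.8 were not edited and still promise the curves.

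A reader might infer that the SAP censors deaths and that the curves therefore overstate incidence as a matter of fact. The text does not support this: it is silent on death. The larger figures above hold only if deaths are censored; if they stayed in the risk set to month 24, death would add no bias. What the SAP does state outright is the censoring of the other exits.

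A reader might also extend the overstatement to all three curves. The explant rule does not censor transplant, recovery or exchange, and death may be an event there. Against that reading, the patient-year rule in SAP Appendix 11.1 lists explant and death as separate ends of follow-up. The documents leave the definition unsettled.

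Three further points are fair. The tabulated percentages do not carry this bias, though they ignore incomplete follow-up. No hypothesis is tested on these endpoints (Protocol 12.6, SAP 7.1). And Protocol 12.6 itself calls for Kaplan-Meier for time-to-event outcomes, so the SAP follows the protocol. That explains the choice of method but does not make the censoring of competing exits valid.

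**Conclusion.** The point holds, at minor severity. The transplant and exchange curves are told to censor exits that compete with the event, and none of the three curves says what to do with a death on the pump. If deaths are censored, 24-month incidence is overstated by a factor of roughly 1.17 to 1.29. In the two-interval model this is 1.2 to 11.6 percentage points for true incidences of 5% to 40%. At 6 months it is under one point for the same scenarios (for example, 10.0% plots as 10.9%).

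These sizes rest on the plan's 15% and 30% mortality, on assumed event frequencies and timing, and on hazards in constant ratio within each interval. For explant the fault is an unsettled event definition, and the same factor should not be applied to it. The primary endpoint, the 24-month survival test, the sample size and the power are unaffected.

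**What to change.** Choose one of two routes.

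1. **Strike the curves** in SAP 8.8.4.7 and 8.8.4.8 so that those sections agree with SAP 5.2.
2. **Keep them as cumulative incidence.** Replace the Kaplan-Meier displays with Aalen-Johansen estimates. Treat death on device and the other exits from MVAD support as competing events. Censor only withdrawal, loss to follow-up and end of follow-up. Reconcile Protocol 9.2, Protocol 9.4.9 and SAP 8.8.4.8 on whether pump removal at death counts as an explant in this analysis, and write the answer into the explant event definition.

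The first route costs a few lines of SAP text. The second costs SAP wording, a recorded and justified change from the Kaplan-Meier method in Protocol 12.6 (Protocol 12.1 requires departures to be reported), and a different SAS routine. The plotted incidences would be lower than the Kaplan-Meier versions and, with complete follow-up, would agree with the tabulated percentages.
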